# **GENERAL GUIDANCE**

Scheduled visits that cannot be conducted in person at a study-site will be performed remotely/virtually to the extent possible or may be delayed until such time that on-site visits can be resumed. At each contact, participants will be interviewed to collect safety data. Participants will also be questioned regarding their general health status.

Every effort should be made to adhere to protocol-specified assessments for participants on study intervention, including follow-up. Modifications to protocol-required assessments may be permitted after consultation between the participant and investigator, and with the agreement of the Sponsor. Missed assessments/visits will be captured in the clinical trial management system for protocol deviations. Discontinuations of study interventions and withdrawal from the study should be documented with the appropriate prefix (eg, "COVID-19-related" or other in accordance with Sponsor recommendations) in the case report form.

The Sponsor will continue to monitor the conduct and progress of the clinical study, and any changes will be communicated to the sites and to the health authorities according to local guidance. If a participant has tested positive for a pandemic infection, the investigator should contact the Sponsor's responsible medical officer to discuss plans for study intervention and follow-up. Modifications made to the study conduct as a result of the pandemic should be summarized in the Clinical Study Report.

#### **GUIDANCE SPECIFIC TO THIS PROTOCOL:**

These emergency provisions are meant to ensure the safety of participants on study while site capabilities are compromised by pandemic restrictions. As restrictions are lifted, sites should revert to original protocol conduct as soon as feasible.

Enrollment of new participants may be halted at the Sponsor's discretion and restarted once the situation permits. The investigator's assessment of the risks versus benefit, depending on the situation at their particular site and the ability to monitor the safety of participants must be considered when restarting enrollment at a specific site.

The following provisions are being implemented by the Sponsor with respect to the following protocol mandated procedures to mitigate the impact of a pandemic:

- 1. Study intervention
- 2. Management of discontinuations and withdrawals due to a pandemic
- 3. Options for efficacy and other assessments
- 4. Options for safety assessments
- 5. Handling of missed assessments, visits or doses
- 6. Management of participants with COVID-19 infection
- 7. Statistical considerations

# 1. Study Intervention

# a. Study Intervention Administration: Home- or Self-administration

Study intervention should be continued if, in the assessment of the investigator, it does not result in risk to the participant. Remote medical consultation and alternatives to study medication dispensing, administration, and clinical safety laboratory assessments (including home health nursing) will allow continued study participation for participants in this study. In cases where site visits are not possible under the restrictions and limitations due to a pandemic, participants who have adequate experience and have been trained how to self-inject may self-administer subcutaneous (SC) study intervention outside a study-site (eg, at home) up to the time when pandemic-related restrictions are lifted, and site visits can be resumed. Participants must self-administer the study intervention in compliance with the Instructions for Use (IFU) document at the times instructed by the investigator. Site-staff will contact the participants by phone prior to, and 30 minutes after the administration of the study intervention for evaluation of AEs. The study-intervention must be self-administered only on completion of the phone contact with the site-staff.

Study-site personnel will instruct participants on how to store study intervention for at-home use, and disposal of used syringes. For each administration of study intervention, the time and date of injection, whether study intervention was self-administered, and if so, whether SC administration was complete will be recorded in the study participant drug administration card.

# b. Preparation/Handling/Storage/Accountability

In case site visits are not possible due to the restrictions arising from a pandemic, any participant who will be self-administering study intervention outside of a study-site will receive detailed instructions on how to store study intervention, disposal of used syringes, and handling of unused study material. Participants will also receive a sharps container to dispose of used syringes and will be instructed to return the sharps container and all unused cartons with syringes.

Participants will maintain a record of the time and date of study intervention administrations in the study participant drug administration cards which will be shipped in advance to the participants. Study-site personnel will utilize the study participant drug administration card to ensure compliance and document at-home study intervention administrations in the CRF.

# c. Notes on Shipment of Study Intervention to Participants

If it is necessary to ship the study intervention directly to study participants, shipment by the study-site itself is preferred under this exception due to a pandemic. Shipment should be made in a manner that allows tracking of both transport and delivery. The participant should acknowledge receipt of the shipment to the site (eg, by returning a dated and signed receipt form).

In case adequate shipment by the study-site is not possible (for example, owing to capacity limitations, logistics, or special transport conditions for the study intervention), direct transport by the Sponsor may be accepted in justified exceptional cases, provided that the Sponsor appoints a suitably qualified service provider as trustee. Both the transport and handover conditions for study intervention should be part of the contractual arrangements, so that pharmaceutical drug safety of study intervention as well as protection of the privacy and personal data of participants are adequately safeguarded. The study intervention must be delivered directly to the participant or a person authorized by the participant, and must not be given to neighbors or deposited at a storage location. Written confirmation of dose and dose regimens by the investigator should also be obtained prior to shipment.

The personnel of the service provider in charge of the transport should be trained and instructed accordingly. As personal data are transferred to the service provider, this requires a contract of assignment with the Sponsor or legal representative.

For direct shipment of study intervention to participants, instructions on storage and return of used and unused study intervention should be provided to participants. When shipped by study sites, the receipt, consumption and return of study intervention must be documented in a form that allows the study-site to meet its documentation requirements (ie, drug accountability), as defined in ICH GCP 4.6.3.

# d. Discontinuation of Study Intervention

If at any time the safety of a participant is considered to be at risk, study intervention will be temporarily or permanently discontinued, while every effort should be made to maintain follow-up on study.

The benefit of continuing study treatment should be considered by the investigator for each individual participant, considering the potential impact of reduced direct clinical supervision on a participant's safety. A temporary interruption of study intervention might be considered based on investigator's discretion and documented.

Discontinuations of study interventions due to pandemic-related reasons should be documented with a prefix (eg, "COVID-19-related" or in accordance with Sponsor recommendations) in the CRF.

# 2. Management of Discontinuations and Withdrawals due to a Pandemic

Withdrawal from the study due to pandemic-related reasons should be documented with a prefix (eg, "COVID-19-related" or in accordance with Sponsor recommendations) in the CRF. Study intervention assigned to the withdrawn participant may not be assigned to another participant. If the sample size is not achieved due to pandemic-related reasons or other emergency situations, enrollment of additional participants will be considered by the Sponsor.

# 3. Options for Efficacy and Other Assessments

To safely maintain participants on study treatment while site capabilities are compromised by pandemic or other emergency restrictions, participants may have tele-health visits (conducted via phone or video conversation per local regulation) until such time that on-site visits can be resumed.

Normal study procedures should be followed for the applicable visit as closely as possible, however it is recognized that remote visits may be limited to the collection of the following data:

- Concomitant therapy checks
- PROs

Patient-reported outcomes (PRO) questionnaires in paper format may be shipped to participants along with instructions for completion. The PROs must be completed on the day of the scheduled visit prior to administration of the study intervention and any tests, procedures or consultations and sent to the investigator by appropriate means per Sponsor instructions.

Actual dates of assessments will be recorded by the participants and transcribed to the CRF. Missed assessments/visits will be captured in the clinical trial management system for protocol deviations.

If assessments are not possible as outlined in the Schedule of Activities, missed assessments should be documented as a deviation related to the pandemic and be made up as soon as possible.

# 4. Options for Safety Assessments

All efforts should be done to perform the following safety assessments, when applicable:

- Vital signs
- Weight
- Early Detection of Active Tuberculosis (per protocol Section 8.2.5)

- Urine pregnancy testing
- Safety assessments related to study intervention administration, including injection-site reactions evaluation
- Clinical Safety Laboratory Assessments (including through home collection of samples or at certified local laboratory, where possible)

At each contact/remote visit, participants will be interviewed to collect safety data per the list above. At drug administration time-points, site-staff will contact the participants by phone prior to, and 30 minutes after the administration of the study intervention (when done at home) for evaluation of AEs including injection-site reactions.

In cases where participants receive SC injections outside the study-site during the treatment period, participants are requested to contact their treating physician as soon as they experience any untoward medical occurrence. The treating physician should consider reporting any AEs.

Home testing may be employed for urine pregnancy tests. The urine pregnancy test will be shipped in advance to the participants. For women of childbearing potential, a negative pregnancy test must be recorded on the study participant drug administration card before self-administering the study intervention.

Clinical laboratory safety monitoring may be performed using home collection of samples or at a certified local laboratory rather than at the central laboratory. A copy of the external laboratory report should be reviewed by the investigator and retained, along with reference ranges, for source documentation and captured in the CRF.

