#### **Serious Adverse Events**

All SAEs occurring during the study must be reported to the appropriate Sponsor contact person by study-site personnel within 24 hours of their knowledge of the event.

Information regarding SAEs will be transmitted to the Sponsor using the Serious Adverse Event Form and Safety Report Form of the CRF, which must be completed and reviewed by a physician from the study-site, and transmitted to the Sponsor within 24 hours. The initial and follow-up reports of a SAE should be transmitted electronically or by facsimile (fax) via a secure transmission system.

Any possible Hy's law case (AST or ALT  $\geq$ 3x ULN together with bilirubin  $\geq$ 2X ULN or INR >1.5) is considered an important medical event and must be reported to the sponsor in an expedited manner using the Serious Adverse Event form, even before all other possible causes of liver injury have been excluded. The INR criterion is not applicable to participants receiving anticoagulants.

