## 8.3.3. Regulatory Reporting Requirements for Serious Adverse Events

The Sponsor assumes responsibility for appropriate reporting of AEs to the regulatory authorities. The Sponsor will also report to the investigator (and the head of the investigational institute where required) all suspected unexpected serious adverse reactions (SUSARs). The investigator (or Sponsor where required) must report SUSARs to the appropriate Independent Ethics Committee/Institutional Review Board (IEC/IRB) that approved the protocol unless otherwise required and documented by the IEC/IRB.

All AEs will be recorded in the CRF and will be reported to the Sponsor as described under All Adverse Events in Section 8.3.1, Time Period and Frequency for Collecting Adverse Event and Serious Adverse Event Information.

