#### 8.4. Treatment of Overdose

No clinical studies in humans have been conducted to assess a toxic threshold for guselkumab. The highest single SC dose of guselkumab investigated in humans was 300 mg. The maximum IV dose (10 mg/kg) in humans was 987 mg.

In the event of an overdose (any dose greater than that prescribed for the study), the investigator or treating physician should:

- Contact the Medical Monitor immediately.
- Closely monitor the participant for AE/SAE and appropriate symptomatic treatment instituted immediately.

Decisions regarding dose interruptions or modifications will be made by the investigator in consultation with the Medical Monitor based on the clinical evaluation of the participant.

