#### SOURCE DOCUMENTS

At a minimum, source documents consistent in the type and level of detail with that commonly recorded at the study-site as a basis for standard medical care must be available for the following: participant identification, eligibility, and study identification; study discussion and date of signed informed consent; dates of visits; results of safety and efficacy parameters as required by the protocol; record of all AEs and follow-up of AEs; concomitant medication; intervention receipt/dispensing/return records; study intervention administration information; and date of study completion and reason for early discontinuation of study intervention or withdrawal from the study, if applicable.

The author of an entry in the source documents should be identifiable.

Specific details required as source data for the study and source data collection methods will be reviewed with the investigator before the study and will be described in the monitoring guidelines (or other equivalent document).

The following data will be recorded directly into the CRF and will be considered source data:

- Race
- Blood pressure and pulse/heart rate

- Height and weight
- Details of physical examination

The minimum source documentation requirements for Section 5.1, Inclusion Criteria and Section 5.2, Exclusion Criteria that specify a need for documented medical history are as follows:

- Referral letter from treating physician or
- Complete history of medical notes at the site
- Discharge summaries

Inclusion and exclusion criteria not requiring documented medical history must be verified at a minimum by participant interview or other protocol-required assessment (eg, physical examination, laboratory assessment) and documented in the source documents.

An eSource system may be utilized, which contains data traditionally maintained in a hospital or clinic record to document medical care (eg, electronic source documents) as well as the clinical study-specific data fields as determined by the protocol. This data is electronically extracted for use by the Sponsor. If eSource is utilized, references made to the CRF in the protocol include the eSource system but information collected through eSource may not be limited to that found in the CRF.

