# **PROCEDURES**

#### **All Adverse Events**

All AEs, regardless of seriousness, severity, or presumed relationship to study intervention, must be recorded using medical terminology in the source document and the CRF. Whenever possible, diagnoses should be given when signs and symptoms are due to a common etiology (eg, cough, runny nose, sneezing, sore throat, and head congestion should be reported as "upper respiratory infection"). Investigators must record in the CRF their opinion concerning the relationship of the adverse event to study therapy. All measures required for adverse event management must be recorded in the source document and reported according to Sponsor instructions.

For all studies with an outpatient phase, including open-label studies, the participant must be provided with a "wallet (study) card" and instructed to carry this card with them for the duration of the study indicating the following:

- Study number
- Statement, in the local language(s), that the participant is participating in a clinical study

- Investigator's name and 24-hour contact telephone number
- Local Sponsor's name and 24-hour contact telephone number (for medical personnel only)
- Site number
- Participant number

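### Appendix 15 sends home-dosed participants to an undefined treating physician for whom adverse event reporting is optional, out of line with the protocol's mandatory, site-based reporting

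*Protocol*

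**What the plan says.** Protocol Appendix 15, item 4 (Options for Safety Assessments), covers injections given outside the site while pandemic restrictions apply. In that case "participants are requested to contact their treating physician as soon as they experience any untoward medical occurrence". The next sentence reads "The treating physician should consider reporting any AEs". It gives no recipient, deadline or form.

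The main protocol is firmer:

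- Section 8.3.1 requires all adverse events, serious or not, to be reported from consent to the last study-related procedure.
- Also in Section 8.3.1, serious events "must be reported to the appropriate Sponsor contact person by study-site personnel within 24 hours of their knowledge of the event". They go on a form "which must be completed and reviewed by a physician from the study-site, and transmitted to the Sponsor within 24 hours".
- Section 8.3.3: "All AEs will be recorded in the CRF and will be reported to the Sponsor".
- Appendix 13, Procedures: "All AEs, regardless of seriousness, severity, or presumed relationship to study intervention, must be recorded".

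Appendix 15 does not suspend these rules. It restates that standard event reporting applies only in item 6, for participants with SARS-CoV-2 infection. Item 4 has no such sentence.

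**The concern.** Two things in item 4 are out of step with the rest of the protocol: who is told first, and whether that person has to pass the information on. Everywhere else, reporting is compulsory and runs through the site.

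What is at stake is how soon the site learns of an event that begins after the post-dose telephone call. The 24-hour period for serious events starts when site personnel know of the event, not when it happens. Prompt notice also matters for stopping treatment. Section 7.1 requires guselkumab to be discontinued for serum-sickness-like reactions 1 to 14 days after an injection, well outside a 30-minute call, and for serious infections.

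**Working it through.** No sample size, power or rate is involved, so the check compares texts and adds one count.

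**Step 1: who is the treating physician?** Section 2 explains the terms study intervention, Sponsor and participant, but not this one. The other uses found are:

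- Section 6.5.2, on whether corticosteroids have adequate alternatives. This does not settle the meaning.
- Section 8.4, on overdose: "the investigator or treating physician should" take certain steps. The two are listed as alternatives.
- Appendix 12, Source Documents: "Referral letter from treating physician". Here it is the author of a letter to the site.
- Item 4 itself names the investigator when it means the investigator, for example for review of external laboratory reports.

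The term therefore need not mean the investigator, and the wording leans towards someone else. It does not settle the matter.

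**Step 2: the investigator reading.** One person is told to consider reporting by item 4, and is bound to record and report by Sections 8.3.1 and 8.3.3 and Appendix 13. The wording conflicts. There is no delay, because the site already knows.

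**Step 3: the outside-doctor reading.** The compulsory rules bind study-site personnel and investigators. A softer verb for a doctor outside the study does not contradict them. The weakness is the route: the requested first contact is not the site, and the onward step is optional. The 24-hour clock waits for the site's knowledge.

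The wording conflict and the possible delay thus arise on different readings, never together.

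**Step 4: how much dosing is exposed?**

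- Scheduled doses: Weeks 0, 4, 12, 20 and 28, so 5.
- Week 0 is always given at the site (Section 6.1), so home doses are at most 5 − 1 = 4.
- Site calls per home dose: one before and one 30 minutes after (Appendix 15, items 1 and 4), so at most 2 × 4 = 8 calls per participant.

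This is a ceiling. Item 1 allows home dosing only when site visits are not possible and the participant is experienced and trained in self-injection. The documents do not show that any home dose was given.

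**Step 5: what limits the delay?**

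- Participants report events for the duration of the study (Section 8.3).
- Safety interviews take place at each contact (Appendix 15, General Guidance and item 4).
- Events are recorded at the dosing visits and at the Final Safety Visit (Section 8).
- The wallet card in Appendix 13 gives the investigator's 24-hour number, a 24-hour local Sponsor number reserved for medical personnel, and the study, site and participant numbers.

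The added delay is zero if the treating physician is the investigator, or if the participant also calls the site. Otherwise it lasts until someone tells the site, at latest the next site contact at which the event is mentioned. Visit spacing is the same for every participant, so no number of added days can be attributed to item 4.

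**The case against.** The best defence is that item 4 adds a contact and removes nothing. It does not tell participants to avoid the site, and every ordinary safeguard continues. A protocol cannot place a duty on a doctor who is not part of the study, so a soft verb is natural for one. A participant dosed at the site also goes home and may tell another doctor first, and then too the clock starts only with the site's knowledge. Appendix 15 also calls its contents recommendations.

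Most of this stands, and it rules out three stronger conclusions that a reader might draw.

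- *That item 4 flatly contradicts the 24-hour rule.* It does not on the outside-doctor reading. On the investigator reading the stricter rules still bind that person.
- *That an outside doctor has no way to reach the study.* The wallet card gives such a doctor lines to both the investigator and the local Sponsor.
- *That events would be lost and the adverse event rate, a secondary endpoint, distorted.* The safeguards listed above largely protect eventual capture.

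What the defence does not explain is why the one instruction written for home dosing names someone other than the site and makes reporting a matter for consideration. In ordinary conduct a participant may happen to call another doctor first. Here the protocol asks for it, if the term means an outside doctor. If the general rules prevail in any case, the sentence does no work and can only mislead.

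**Conclusion.** The point holds as a minor defect in safety-reporting wording, confined to off-site dosing during a pandemic. On the investigator reading, optional wording sits against compulsory rules. On the outside-doctor reading, the site may hear late, so the serious-event clock may start late. On either reading the instruction is weaker than the protocol's own rule.

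The size cannot be quantified from the documents. The exposed case is an event starting more than 30 minutes after a home dose, with a ceiling of 4 of 5 doses per participant. SAP Section 1.2 records that the study was discontinued on 31 May 2023, with only final efficacy and final safety visits to be scheduled after that date. There is no basis for claiming an effect on collected data, on the adverse event rate or on the efficacy analysis.

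The conclusion assumes that Section 8.3 and Appendix 13 remain in force for home-dosed participants. That follows from the absence of any waiver in Appendix 15, not from an express statement in item 4.

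**What to change.** In Appendix 15, item 4, replace the two sentences on injections outside the site with one:

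*Participants who receive SC injections outside the study-site should contact the study site as soon as they experience any untoward medical occurrence, in addition to seeking any urgent care they need, and the investigator must record and report all AEs and SAEs as in Section 8.3.1 and Appendix 13.*

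This settles both readings and keeps access to local care. It needs no new visits, calls, forms or staff. With the study closed, its practical use is mainly for any later protocol that reuses this appendix.
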